4.3.2 Safety follow-up

If there are no ongoing SAE/AEs at the time of study medication discontinuation, the safety follow-up with the patient 30 (± 7) days after discontinuation of study medication can be done through telephone contact, capturing any new SAEs/AEs and concomitant meds including new therapy. The primary purpose is to follow-up any AEs ongoing at the time of discontinuation and to assess any new AEs that may have occurred since discontinuation. Any AE/ SAE/ abnormal laboratory findings that are ongoing at the time of study treatment discontinuation or any new treatment related events within 30 days of the last study treatment must be followed up to resolution or until the event becomes stable (or returns to baseline) or is unlikely to resolve further in the opinion of the investigator.

AstraZeneca retains the right to request additional information for any patient with ongoing AE(s)/SAE(s) at the end of the study, if judged necessary.

4.3.3 Follow-up for second progression on subsequent anti-cancer therapy after PD by RECIST 1.1 (PFS2)

Following discontinuation of study medication for PD by RECIST 1.1 as determined by investigator assessment, patients that started on subsequent therapy post-progression will continue to be followed at least every 12 weeks by investigator assessment for documentation of second progression. Subsequent therapy and OS will also be collected. Determination of PD for PFS2 will be by institutional call only. Patients who choose to continue on study therapy after the investigator confirmed PD will not be considered to have a second PFS-event until they have discontinued study medication and started subsequent anti-cancer therapy.

4.3.4 Overall survival follow-up

The OS period begins following determination of PFS2 by institutional call. In the OS follow-up period, all subsequent anti-cancer therapies will be documented by site personnel at least every 12 weeks until death, lost to follow-up, withdrawal of consent, or end of study, whichever comes first.

The status of ongoing, withdrawn (from the study) and “lost to follow-up” patients at the time of an OS analysis should be obtained by the site personnel by checking the patient’s notes, hospital records, contacting the patient’s general practitioner and checking publicly available death registries. In the event that the patient has actively withdrawn consent to the processing of their personal data, the vital status of the patient can be obtained by site personnel from publicly available resources, where it is possible to do so under applicable local laws. Sites have 5 days following the DCO for the final survival analyses to contact patients and provide complete survival data.

4.3.5 Patient management post-final analysis

Stopping criteria for the final analysis are defined in Section 9.3.

Patients receiving study drug, either savolitinib or sunitinib, will be allowed to remain on treatment for as long as they are deriving clinical benefit, in the opinion of investigator(s) or until meeting any discontinuation criteria defined in Section 3.8.

Patients will be monitored in accordance with the investigator’s standard clinical practice and national product label (for patients being treated with sunitinib). Dispensing of study treatment post-final analysis will be done outside of IVRS/IWRS. At routine clinic visits, patients will return partially used and unused medication, and a thorough drug accountability assessment will be performed at the site.

AstraZeneca will collect information (during the treatment period and for 30 (\pm 7) days after discontinuation of study medication) on SAEs, overdose and pregnancy (as per Section 6.3) via paper and emailed (preferably) or faxed directly to Tata Consultancy Services Data Entry Site (DES) (also known as AZ DES). Drug accountability information will be recorded in the source documents.

If an investigator learns of any SAEs, including death, at any time after a patient has completed the study, and he/she considers there is a reasonable possibility that the event is causally related to the investigational product, the investigator should notify AstraZeneca Patient Safety. Additionally, as stated in Section 6.3, any SAE or non-serious AE that is ongoing at the time of this data cut-off, must be followed up to resolution unless the event is considered by the investigator to be unlikely to resolve, or the patient is lost to follow-up.

5. STUDY ASSESSMENTS

The Web Based Data Capture (WBDC) system will be used for data collection and query handling. The investigator will ensure that data are recorded on the electronic Case Report Forms as specified in the Clinical Study Protocol and in accordance with the instructions provided.

The investigator ensures the accuracy, completeness and timeliness of the data recorded and of the provision of answers to data queries according to the Clinical Study Agreement. The investigator will sign the completed electronic Case Report Forms. A copy of the completed electronic Case Report Forms will be archived at the study site.

5.1 Efficacy assessments

5.1.1 Tumour assessments by CT or MRI scans (RECIST 1.1)

The baseline assessment will be performed no more than 28 days prior to the date of randomisation and as close as possible to the start of study treatment. Following the baseline assessment, subsequent tumour assessments should be performed every 6 weeks at the start of each cycle (± 7 days) during the first year and then every 12 weeks (± 1 week) thereafter up to the time of BICR-confirmed PD. Anonymised copies of all CT/MRI scans done for tumour evaluation will be sent to an AstraZeneca appointed Contract Research Organisation (CRO) for blinded independent central review as soon as possible following completion of each scan (see Section 5.1.2). All scans should be evaluated using RECIST assessments until BICR-confirmed progressive disease.

At baseline, the imaging modalities used for RECIST assessment will be contrast-enhanced CT (MRI where CT is contraindicated) scans of the chest, abdomen and pelvis with other regions as clinically indicated for the assessment of disease. The same imaging modality should be used for subsequent follow-up assessments and will cover chest (in those patients with disease in the chest or upper abdomen lymphadenopathy at baseline), abdomen and pelvis with any other regions imaged at baseline where disease was present. Any other sites where new disease is suspected should also be appropriately imaged.

Radiological examinations performed in the conduct of this study should be retained at the site as source data.

It is important to follow the assessment schedule as closely as possible. If scans are performed outside of the scheduled visit ± 7 -day window interval and the patient has not progressed, every attempt should be made to perform the subsequent scans at their scheduled time points. This schedule is to be followed in order to minimise any unintentional bias caused by some patients being assessed at a different frequency than others.

5.1.2 Tumour evaluation

RECIST 1.1 criteria will be used to assess patient response to treatment by determining progression free survival (PFS) times, objective response rates (ORR) and duration of response (DoR) and disease control rate (DCR). The RECIST 1.1 guidelines for measurable, non-measurable, target and non-target lesions and the objective tumour response criteria (complete response, partial response, stable disease or progression of disease) are presented in Appendix F.

Categorisation of objective tumour response assessment will be based on the RECIST 1.1 criteria of response: complete response (CR), partial response (PR), stable disease (SD), progression of disease (PD), and not evaluable (NE). Target lesion (TL) progression will be calculated in comparison to when the tumour burden was at a minimum (ie, smallest sum of diameters previously recorded on study). In the absence of progression, tumour response (CR, PR, SD or NE) will be calculated in comparison to the baseline tumour measurements obtained prior to randomisation.

If the investigator is in doubt as to whether progression has occurred, particularly with response to NTL (non-target lesion) or the appearance of a new lesion, it is advisable to continue treatment until the next scheduled assessment or sooner if clinically indicated and reassess the patient's status. If repeat scans confirm progression, then the date of the initial scan should be declared as the date of progression.

To achieve 'unequivocal progression' on the basis of non-target disease, there must be an overall level of substantial worsening in non-target disease such that, even in presence of SD or PR in target disease, the overall tumour burden has increased sufficiently to merit discontinuation of therapy. A modest 'increase' in the size of one or more non-target lesions is usually not sufficient to qualify for unequivocal progression status.

5.1.3 Central reading of scans/BICR

An independent review of all scans used in the assessment of tumours using RECIST 1.1 will be conducted. All imaging assessments including unscheduled scans will be collected on an ongoing basis and sent to an AstraZeneca appointed CRO following completion of each scan. All scans will be read by BICR after notification of Progressive Disease by the investigator. If PD is not centrally confirmed, each subsequent scan will be read by BICR once it is received and processed by the CRO.

Every effort should be made by the institution to send each scan to the CRO as quickly as possible, so that Quality Control can be performed and the scans will be ready for review by the radiologists at the time that the patient develops Progressive Disease by institutional call. This scan, in particular, should be sent to the designated vendor without delay after acquisition, to minimise the turn-around time for confirmation of PD by BICR. Depending on

the speed and completeness of image submission to the sponsor-designated vendor, the turn-around time should generally be within 10 days.

During verification of the institution's diagnosis of radiographic progression by BICR, participants may continue to receive study treatment. The decision whether to continue or to withhold study treatment will be at the discretion of the investigator, but if not medically contra-indicated, patients should be encouraged to not start alternative anti-cancer therapy until confirmation of PD by BICR. If PD is not confirmed by BICR, the patient may continue/resume study treatment and must continue to undergo assessments as per Table 1, including scans at 6-week intervals (or sooner if felt to be medically indicated) until PD is confirmed by BICR. Those who begin subsequent non-study anti-cancer therapy prior to BICR-confirmed PD should continue to undergo tumour assessments, and sites must send each scan to the sponsor-designated vendor until PD is confirmed by BICR.

After the primary PFS analysis, central review of scans will no longer be required and investigators will be advised when to stop sending copies of the scans to the CRO conducting the central review. The primary analysis of PFS for this study will be based on confirmation of PD using RECIST 1.1 by BICR.

5.2 Safety assessments

5.2.1 Laboratory safety assessments

Blood and urine samples for determination of clinical chemistry, haematology, and urinalysis will be taken at the times indicated in the Study Plan (see Table 1).

The following safety laboratory variables will be measured:

Table 2 Standard Laboratory Safety Assessment Panel

Clinical chemistry safety	Haematology
S/P-Albumin	B-Absolute leucocyte differential count
S/P-Alkaline phosphatase ²	B-Eosinophils
S/P-ALT ²	B-Haemoglobin
S/P-Amylase	B-Leucocyte cell count
S/P-AST ²	B-Lymphocytes
S/P-Bilirubin, total ^{2,4}	B-Neutrophils
S/P-Calcium, total	B-Platelet count
S/P-Creatinine	Urinalysis
S/P-Free T4 ³	U-Dipstick-Blood
S/P-Glucose	U-Dipstick-Glucose
S/P-HBsAg ⁵ , anti-HBc (qualitative), HBV DNA ⁶ , HCV antibody, HCV RNA ⁷	U-Dipstick-Ketones
S/P-Lactate dehydrogenase ³	U-Dipstick- Leukocyte esterase or Leukocyte count
S/P-Magnesium	U-Dipstick-Protein ¹
S/P-Phosphate	
S/P-Potassium	
S/P-Sodium	
S/P-Thyroid Stimulating Hormone ³	
S/P-Total Protein	
S/P-Urea nitrogen	

- ¹ If 3+ or greater proteinuria is identified by dipstick assessment, a 24-hour urine collection for formal quantification of the level of protein excretion should be performed
- ² Designates tests that are considered liver function tests (LFTs) and are to be done weekly x 9 and then at the start of every course thereafter. Guidelines for management of hepatotoxicity are in section 6.8.1.2 for savolitinib and section 6.8.2 for sunitinib
- ³ Thyroid function studies and LDH are to be done at the main study (Part 2) screening visit, and at the start of every cycle thereafter
- ⁴ If total bilirubin is >2x ULN, then fractionate into indirect and direct bilirubin
- ⁵ If the HBsAg test is negative, the anti-HBc test should be still performed
- ⁶ HBV DNA test should be available for all patients that have had a previous HBV infection or are positive for HBsAg
- ⁷ HCV RNA qualitative test is only needed if the HCV Ab test is positive, and must be negative for the patient to be eligible.

Unscheduled blood or urine samples may need to be taken at the onset and as a part of a follow-up of some SAEs. The results should be added to the clinical trial database.

In case a patient shows an AST or ALT ≥ 3 x ULN and total bilirubin ≥ 2 x ULN please refer to Appendix E 'Actions Required in Cases of Increases in Liver Biochemistry and Evaluation of Hy's Law', for further instructions.

For blood volumes see Section 5.7.12

5.2.2 Physical examination

For timing of individual measurement refer to study schedule (see Table 1).

A complete physical examination will be performed and include an assessment of the following: general appearance, respiratory, cardiovascular, abdomen, skin, head and neck (including ears, eyes, nose and throat), lymph nodes, thyroid, musculoskeletal (including spine and extremities) and neurological systems.

5.2.3 ECG, ECHO/MUGA

5.2.3.1 Resting 12-lead ECG

QTcF evaluation for the main study screening (Part 2) will be done based on triplicate 12 lead ECGs during the Part 2 screening period, every week in the first cycle, every cycle thereafter, and at the end of treatment as indicated in Table 1. Twelve-lead ECGs (triplicate) will be obtained after the patient has been rested in a supine position for at least 5 minutes. The investigator or designated physician will review the paper copies of the 12-lead ECGs. ECGs will be recorded at 25 mm/sec. All ECGs should be assessed by the investigator as to whether they are clinically significantly abnormal / not clinically significantly abnormal. If there is a clinically significant abnormal finding, the investigator will record it as an AE on the eCRF. The original ECG traces must be stored in the patient medical record as source data. A 28-day follow-up assessment will be required if an on-treatment assessment was abnormal at the time of discontinuation of study therapy, to confirm reversibility of the abnormality.

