5.2.4 Vital signs

Vital signs (heart rate, BP, temp) will be performed during the main study (Part 2) screening visit, during study treatment as per Table 1 and as clinically indicated.

Height will be assessed at the main study (Part 2) screening visit only. Weight will be assessed at the Part 2 screening visit, at the beginning of every cycle, and more frequently if clinically indicated. **The dose of savolitinib will not change for patients who started the study at <50 kg (ie, 400 mg), even if their weight increases to ≥50 kg during the course of the study.**

Any changes in vital signs should be recorded as an AE, if applicable.

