6.3.2 Follow-up of unresolved adverse events

Any AE/ SAE/ abnormal laboratory findings that are ongoing at the time of study treatment discontinuation or any new treatment related events within 30 days of last study treatment, must be followed up to resolution or until the event becomes stable (or returns to baseline) or is unlikely to resolve further in the opinion of the investigator. AstraZeneca retains the right

to request additional information for any patient with ongoing AE(s)/SAE(s) at the end of the study, if judged necessary.

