6.3.6 Adverse events based on examinations and tests

The results from the Clinical Study Protocol mandated laboratory tests and vital signs will be summarised in the CSR. Deterioration as compared to baseline in protocol-mandated laboratory values or vital signs or cardiac evaluations should therefore only be reported as AEs if they fulfil any of the SAE criteria or are the reason for discontinuation of treatment with the investigational product.

If deterioration in a laboratory value/vital sign is associated with clinical signs and symptoms, the sign or symptom will be reported as an AE and the associated laboratory result/vital sign will be considered as additional information. Wherever possible the reporting investigator uses the clinical, rather than the laboratory term (eg, anaemia versus low haemoglobin value). In the absence of clinical signs or symptoms, clinically relevant deteriorations in non-mandated parameters should be reported as AE(s).

Deterioration of a laboratory value, which is unequivocally due to disease progression, should not be reported as an AE/SAE.

Any new or aggravated clinically relevant abnormal medical finding at a physical examination as compared with the baseline assessment will be reported as an AE.

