6.8.1.4 Dose modifications for savolitinib-related QTcF prolongation

Dose modifications for savolitinib-related QTcF prolongation are reported in Table 10

Table 10 Dose modifications for savolitinib-related QTcF prolongation

NCI CTCAE toxicity grade	Action
Grade 0, 1, or 2	None
Grade 3	Hold dosing and follow algorithm below

 Patients with QTcF prolongation to >500 msec on at least two separate ECGs If the toxicity does not resolve to QTcF <481msec within 21 days 	
 Consult with a cardiologist to validate ECG finding. Ensure cardiac surveillance and take actions in accordance with clinical standard. Regular ECGs performed until resolution to QTcF <481 msec and then restart drug at one reduced dose level Discontinue study drug and consult with a cardiologist for further management as clinically indicated
Grade 4	

 QTcF \geq501 or >60 msec change from baseline and Torsades de pointes or polymorphic ventricular tachycardia or signs/symptoms of serious arrhythmia 	
 Discontinue study drug and consult with a cardiologist for further management as clinically indicated

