8. STATISTICAL ANALYSES BY ASTRAZENECA

8.1 Statistical considerations

A comprehensive Statistical Analysis Plan (SAP) will be prepared prior to the first subject randomised and any subsequent amendments will be documented, with final amendments completed prior to database lock. The aim of this study is to compare the efficacy and safety of savolitinib versus sunitinib. Analyses will be performed by AstraZeneca or its representatives. All personnel involved with the analysis of the study will remain blinded to aggregated results until database lock and protocol violators identified.

Due to termination of recruitment into SAVOIR, all secondary analyses will be descriptive.

Sample size estimate

Approximately 180 patients were planned to be randomised from 5 to 10 countries worldwide in approximately 50 to 75 sites. Recruitment to the study was closed on 22 November 2018. It is now estimated that approximately 50 patients will be randomised from 7 countries.

The initial assumption was that the true treatment effect had a hazard ratio (HR) of 0.6 (which would have translated to an approximate 3-month improvement in median PFS over an assumed 4-month median PFS for MET-driven patients on sunitinib, assuming PFS was exponentially distributed), 121 PFS events confirmed by BICR would have had to have been observed for the study to have 80% power to show a statistically significant difference in PFS at the two-sided 5% level. The smallest treatment difference that would have been statistically significant at the final analysis was a PFS HR of 0.69. Assuming 67% maturity; 180 patients would have been needed to be randomised. An interim futility analysis of PFS was planned to be conducted when a total of approximately 36 BICR-confirmed PFS events had been observed (30% of 121 PFS events, which was estimated to occur 17 months after the first patient had been randomised). Following IDMC endorsement to terminate recruitment into SAVOIR, the interim analysis will not occur.

[REDACTED]

[REDACTED]

[REDACTED]

Following IDMC endorsement to terminate recruitment into SAVOIR, a sample size-reassessment will no longer be performed.

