8.4.2 Analysis of the secondary variable(s)

Objective Response and Disease Control Rates

ORR and DCR will be presented with a two-sided 95% CIs using Clopper-Pearson method (Clopper and Pearson, 1934). The number and percentage of patients in each response category (CR, PR, SD, PD, NE) will be summarised. Results may be summarised by the IMDC risk category if patient numbers permit.

Duration of response

Kaplan-Meier plots of duration of response in the responding patients will be produced.

Change in tumour size

The best change in target lesion tumour size from baseline (where best change in target lesions size is the maximum reduction from baseline or the minimum increase from baseline in the absence of a reduction) will also be summarised.

Waterfall plots (bar charts) indicating the best percentage change from baseline in sum of the diameters of TLs will be produced. Reference lines at the +20% and 30% change in tumour size levels will be added to the plots, which correspond with the definitions of progression and ‘complete or partial’ response respectively.

Overall Survival

Summaries (number of deaths, medians, and proportion alive at 1 year) and Kaplan Meier plots will be provided.

Time to second progression or death (PFS2)

Summaries (number of 2nd progression events or deaths, medians, and proportion alive at 1 year) and Kaplan Meier plots will be provided.

PRO analyses

Analyses on the FACIT-F, FKSI-19, EQ-5D-5L and PRO-CTCAE will be based on the instruments’ scoring manuals.

Descriptive statistics will be calculated for each scheduled visit/time point in the study, for each trial arm and as a total. These will report the number of patients, the number of EQ-5D questionnaires completed at each visit, the number and proportion responding to each dimension of the EQ-5D-5L. Additionally, summary statistics (eg, n, mean, median, sd, min, max) will be reported for the EQ-5D index score and the EQ-VAS score, and the change from baseline for the EQ-5D index score and the EQ-VAS score.

To support submissions to payers, additional analyses may be undertaken and these will be outlined in a separate Payer Analysis Plan.

Safety analyses

Safety data will not be analysed formally. Standard data summaries will be produced for safety data including (but not limited to):

- Summaries of AEs of any CTCAE grade – summarised by MedDRA preferred term and system organ class and CTCAE grade.
- Summaries of Grade 3 and above AEs.
- SAEs.

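### A new, clinically significant ECG finding that is neither serious nor the reason for discontinuation is an adverse event under Section 5.2.3.1 but not under Section 6.3.6

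*Protocol*

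**What the plan says.** Section 5.2.3.1 of the protocol makes the classification universal: "All ECGs should be assessed by the investigator as to whether they are clinically significantly abnormal / not clinically significantly abnormal". The consequence of a positive classification follows directly: "If there is a clinically significant abnormal finding, the investigator will record it as an AE on the eCRF". Seriousness and discontinuation play no part in it.

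Section 6.3.6 deals with AEs that arise from examinations and tests. For deterioration from baseline in protocol-mandated laboratory values, vital signs or cardiac evaluations, it limits AE reporting to two situations: "cardiac evaluations should therefore only be reported as AEs if they fulfil any of the SAE criteria or are the reason for discontinuation".

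The vital signs section has a recording rule of its own, but a conditional one: "Any changes in vital signs should be recorded as an AE, if applicable". That wording leaves room for Section 6.3.6 to operate. The ECG rule has no such qualifier, and neither Section 5.2.3.1 nor Section 6.3.6 refers to the other.

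**The concern.** Two instructions cover the same ECG and can give opposite answers. QTc prolongation is listed among the identified risks of savolitinib in Section 6.8.1.5, after the positive thorough QT study reported in Section 1.3. AEs are an outcome measure for the safety objective in Section 2.3.

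If a site follows Section 6.3.6, a non-serious ECG event that does not end treatment stays out of the AE tables, including the one described in Section 8.4.2 as "Summaries of Grade 3 and above AEs". The items that Section 6.3.3 collects for each AE, among them worst grade, causality and action taken, are then not collected for that event. The general follow-up duty in Section 6.3.2, under which an ongoing event "must be followed up to resolution or until the event becomes stable (or returns to baseline) or is unlikely to resolve further", covers AEs, SAEs and laboratory findings. It therefore reaches an ECG finding only once that finding has been recorded as an AE. A site that follows Section 5.2.3.1 records all of this.

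**Working it through.** The plan gives no figure to reproduce. The check is whether the two rules really collide, and whether other text settles the matter.

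**Does Section 6.3.6 cover ECGs?** It applies to protocol-mandated cardiac evaluations. Table 1 and its footnote 10 mandate triplicate ECGs at Part 2 screening, weekly in Cycle 1 and every cycle after that. Section 5.2.3 places ECG and ECHO/MUGA under one heading. The natural reading is that ECGs are covered.

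**Where do the rules differ?** Take an on-treatment ECG that has deteriorated from baseline and that the investigator calls clinically significantly abnormal.

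| The finding | Section 5.2.3.1 | Section 6.3.6 |
|---|---|---|
| meets an SAE criterion | AE | AE |
| is the reason for discontinuation | AE | AE |
| is neither | AE | not an AE |

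The conflict is confined to the third row.

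**Can the third row occur?** Table 10 in Section 6.8.1.4 allows for it. For QTcF above 500 msec on at least two ECGs, savolitinib is held and a cardiologist is consulted. The next step is "Regular ECGs performed until resolution to QTcF <481 msec and then restart drug at one reduced dose level". If the value comes down within 21 days, treatment is not discontinued. Unless the investigator also judges the event serious, it falls in the third row.

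**Does other text in Section 6.3.6 resolve it?** It does not:
- The sentence on accompanying signs and symptoms names laboratory values and vital signs only, and it makes the symptom the AE. An ECG change without symptoms gains nothing from it.
- The sentence on clinically relevant deterioration without symptoms is limited to parameters that the protocol does not mandate.
- New physical examination findings have their own provision. ECG findings have none.

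**Scale.** Section 8.1 gives the expected size: "It is now estimated that approximately 50 patients will be randomised from 7 countries". At 1:1 allocation, 50 / 2 = 25 per arm, so one affected patient is 1/25 = 4 percentage points on an ECG-specific AE term. The protocol gives no rate for such findings. Purely as an assumption, 0 to 5 affected patients in an arm would give 0/25 = 0% to 5/25 = 20% under Section 5.2.3.1, against 0% from the same patients under Section 6.3.6. Incidence of any AE would hardly move, because an affected patient counts only if he or she has no other AE. In the savolitinib monotherapy data of Section 1.1.3.4, 198/233 = 85% of patients already had a related AE.

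**The case against.** The strongest reply is that the rules need not collide. Section 6.3.6 never uses the word ECG and does not define cardiac evaluations. Its opening premise, that results will be summarised in the study report anyway, mentions only laboratory tests and vital signs. The phrase could be read as ECHO/MUGA alone. This is possible but strained, given that ECGs are mandated and share a heading with ECHO/MUGA. A second reply is that the ECG-specific *will* beats the general *should*. Many sites may work that way, but no precedence is stated, and the *only* in Section 6.3.6 is a restriction, not a default. Section 6 is also the part of the protocol with which the principal investigator must make all study staff familiar.

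Other parts of the objection stand and limit the point:
- A QTcF above 500 msec that leads to a hold and a cardiology consultation could well be judged an important medical event under Section 6.2 and Appendix A, and would then be an AE under both rules. Appendix A adds that stopping a drug does not by itself make an event serious, so the gap narrows but does not close.
- Lower-grade QTcF prolongation, for which Table 10 asks no action, need not be clinically significant at all, so it is not a reliable example.
- Follow-up does not rest on AE status alone. Section 5.2.3.1 requires a 28-day assessment when an on-treatment ECG was abnormal at discontinuation, and Table 10 requires ECGs until QTcF has recovered. Dose reductions are logged in IVRS/IWRS in any case (Table 1, footnote 22).

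A reader might infer biased recording between arms, because treatment is open label and Table 10 applies to savolitinib only. The protocol does not support that. The ECG schedule and both recording rules are the same in the two arms, Table 10 governs dosing and not recording, and sunitinib has a hold-and-reduce rule of its own in Table 11. Different recording by arm is possible but is not shown.

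**Conclusion.** The contradiction is real, and it is confined to new, clinically significant ECG findings that are neither serious nor the reason for discontinuation. It rests on reading cardiac evaluations as including the mandated ECGs, which is the natural reading. The consequence is possible inconsistent capture of ECG-related AE terms and their attributes in safety tables that are descriptive only. The count is unknown, and the 4-point step applies to an ECG-specific term, not to overall AE incidence.

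It would go too far to infer that QTc safety data are lost or that patients go unmonitored: Section 8.4.2 still summarises ECG data, and the follow-up ECGs described above do not depend on AE status. PFS, its error rate and its power are not touched. The point deserves correction because the narrower rule, followed as written, leaves out non-serious events of an identified risk, and because the remedy is small.

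**What to change.** Add one sentence to Section 6.3.6: *Exception: an ECG finding the investigator assesses as clinically significantly abnormal is recorded as an AE whether or not it is serious or leads to discontinuation (Section 5.2.3.1).* This keeps the wider rule, which suits an identified QTc risk.

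Before database lock, have sites reconcile ECGs already marked clinically significantly abnormal against the AE pages and enter any that are missing. Section 5.2.3.1 keeps the original traces as source data in the medical record, so the check can be made there if needed.

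The cost is one sentence, one query round for about 50 patients and a few added non-serious AEs. Recruitment is closed, but randomised patients may stay on treatment and remain under the study plan, so the clarification also serves ECGs still to come.
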